The proposed study will extend these results by including both sexes and extend our analysis of the relationship of baseline drinking to cope (DTC) and anxiety by adding baseline standardized questionnaires measuring trait anxiety (STAI), early life adversity (ACES), and a perceived stress scale (PSS) which in other settings was more predictive of health care utilization than stressful life event counts (Cohen, Kamarck et al. 1983). Women are expected to have a greater likelihood of elevated DTC, ACES, trait anxiety scores (Smith and Randall 2012) which will enrich our sample in subjects potentially more responsive to dutasteride vs. pbo. We will use separate randomizations for women vs. men and include dichotomized scores for DTC and *FKBP5* risk allele carrier status in our URN randomization to balance for these potential predictors of efficacy. This study may identify easy to score pre-treatment measures such as the CDMQ, ACES, STAI, PSS and genotype that could be clinically useful for making personalized treatment recommendations regarding use of dutasteride to reduce heavy drinking.

2.C. Experimental Approach / Research Plan

2.C.1. General Design: The study will be conducted in the UCHC Clinical Research Center (CRC) clinic. Random assignment to initial treatment group and double-blind conditions will be maintained throughout the study. The study consists of two 12-week phases (**Table 1**), the first being a 12-week parallel-groups comparison of dutasteride and pbo to evaluate the safety and efficacy of dutasteride 1 mg/day in reducing the likelihood of drinking and heavy drinking in a sample of treatment-seeking men and women with AUD. In the second 12-week phase, responders in phase 1 (defined as a ≥60% reduction in SD/wk for weeks 9-12 compared with screening) will continue on their initial medication assignment, while non-responder subjects treated with placebo will cross over to dutasteride, and non-responder subjects treated with dutasteride will cross over to naltrexone. This design maintains double blind conditions in both phases 1 and 2 and is innovative. This design will: i) promote retention and recruitment, as subjects who do not respond to treatment in phase 1 will cross-over to an active FDA approved medication for AUD, ii) provide two comparisons to examine dutasteride efficacy, a between-subjects

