as to whether events occurred before age 6, between ages 6 and 17, above age 18 or within the past year. We previously reported an interaction of FKBP5 genotype and trauma measured with the TESI on drinking in a large college student sample (Lieberman, Armeli et al. 2016). Presence or absence of childhood trauma will be evaluated for main and interactive effects with FKBP5 genotype on predicting treatment outcomes; g) Adverse Child Experiences Scale (ACES) The ACES assesses early life stress in the form of childhood exposure to adverse experiences and a risky family environment (Felitti, Anda et al. 1998). This 17 item questionnaire probes childhood exposures including psychological abuse, physical abuse, sexual abuse, substance abuse within the family, mental illness within the family, violence toward mother, and criminal behavior in the household. Felitti et al. (Felitti, Anda et al. 1998) found that in a large sample of adults belonging to a HMO, more than half endorsed at least one category of childhood exposure. Individuals who had experienced four or more categories of childhood exposure had 4 to 12-fold increased risk for alcoholism, drug abuse, depression and risky sexual behavior. Scores for the ACES will be evaluated for main and interactive effects with the FKBP5 genotype on predicting treatment outcomes.

2.C.6.b.2. Areas assessed daily during the active treatment period: IVR will be used to collect daily subjective ratings of alcohol-related expectancies, craving, anxiety/tension, and self-efficacy to reduce drinking, as well as drinking amounts. To reduce subject burden for daily IVR in this 24-wk study, we will use IVR to capture daily data for the first 4 study weeks and the last 4 weeks of both phase 1 and phase 2. The IVR daily drinking data will be used together with bi-weekly drinking reports to determine treatment response (60% reduction in drinks/wk) during the last 4 weeks of phase 1 to inform treatment assignment for phase 2. Daily IVR reports will also enable us to address whether study medication moderates associations between daily mood, drinking motives, self-efficacy or daily events and drinking as has been reported using IVR methods for treatment with naltrexone and topiramate (Kranzler, Armeli et al. 2004, Armeli, Feinn et al. 2006). Moderation of relationships between daily mood reports and drinking by medication will be contrasted between baseline and end of phase 1 or 2.

Table 2: Schedule of Assessments

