dutasteride arm non-responders switched to naltrexone to determine whether naltrexone is effective in reducing drinking in dutasteride non-responders. An interrupted time series regression using mixed models will be used (Wagner, Soumerai et al. 2002, mallinckrodt and Lipkovich 2017), where in addition to a variable for week an indicator variable for phase, a second weekly variable that is sequentially coded beginning at phase 2 and the interaction of the two variables will be included in the model. The phase indicator variable will measure change when entering phase 2 and the second weekly variable will measure change in trajectory deviating from phase 1. In addition, a restricted period analysis focusing on the average of the last 4 weeks of phase 1 compared to average of the last 4 weeks of phase 2 will be conducted. This may be more sensitive if the first few weeks of each phase show limited initial response, which would dilute the effects for phase and the interaction for the interrupted regression model. For the first group, dutasteride responders, a non-inferiority test will be used where the non-inferior margin will be 20% above the drinking levels during phase 1. For the latter two groups of non-responders a superiority test will be used.

For aim 3, analysis of drinking outcomes will be repeated including baseline measures of DTC, trait anxiety, perceived stress, adverse child event count and genotype for the *FKBP5* rs1360780 SNP (CC vs. T-carrier) as additional between-subject factors together with the 2- and 3-way interactions of medication condition with DTC, SAI, PSS or ACES measures and *FKBP5* genotype. We will include both Blacks and Caucasians in the pharmacogenetics analysis as our prior study showed similar interactions of *FKBP5* genotype with life stress on drinking measures in both Black and Caucasian college students (Lieberman, Armeli et al. 2016).

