2.C.9.b. Sample size considerations: For Aim 1, the proposed sample size of 160 completing the phase 1 12-week treatment (80 per arm), has 80% power to show statistical significance (α =0.05) for medium-size effects, d=0.4, such as observed in our initial RCT of dutasteride in men (d=0.38 for change in SDs/wk from baseline to last month of treatment comparing dutasteride and pbo n=91]. For Aim 2a, assuming 80% power and α =0.05 and a sample of 40 responder subjects continuing on dutasteride, the non-inferior margin limit would be an increase of 0.67 HDD/wk or 5 SDs/wk during the second 12 weeks dutasteride treatment. For Aim 2b, a sample of 64 placebo non-responders crossing over to dutasteride for phase 2 would have 90% power to detect a medium effect size for reduction in drinking in phase 2 using a within-subjects t-test. For Aim 3, using the GLMPOWER procedure and the between cell effects for the preliminary data presented above (section 2.B.2) for the 2-way interaction of drinking to cope x drug, a sample of 160 subjects in phase 1 would have 80% power to detect the magnitude of this interaction seen in the preliminary dataset.

Table 3. Timeline for recruitment and other study objectives:

Dutasteride AUD#2 protocok V9 (05-18-2022)

IRB NUMBER: 19-147-2 IRB APPROVAL DATE: 02/27/2024

Staff training & study prep										
Patient enrollment & randomizing 5/mo										
3- and 6-month follow-up										
Data entry & cleaning										
Data analysis & Report writing										

Section 3. PROTECTION OF HUMAN SUBJECTS

3.A Risks to Human Subjects

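### The restricted-period comparison for dutasteride responders takes as its reference the same weeks 9-12 that selected them, so a fully maintained response shows an apparent rise, and a non-inferiority test run on it is biased toward failure

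*Combined protocol and SAP*

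**What the plan says.** Section 2.C.1 makes a patient a phase 1 responder by a rule "defined as a ≥60% reduction in SD/wk for weeks 9-12 compared with screening". Section 2.C.6.b.2 confirms that reports from those weeks are used "to determine treatment response (60% reduction in drinks/wk) during the last 4 weeks of phase 1". Dutasteride responders then continue on dutasteride for phase 2.

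The aim 2 part of section 2.C.9.a.2 plans an interrupted time series across both phases. It then adds "a restricted period analysis focusing on the average of the last 4 weeks of phase 1 compared to average of the last 4 weeks of" the second phase. A few lines later it says that for dutasteride responders "a non-inferiority test will be used where the non-inferior margin will be 20% above the drinking levels during phase 1".

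Section 2.C.9.b gives the Aim 2a sample size: 40 responders, 80% power and α of 0.05 (sidedness not stated). It says "the non-inferior margin limit would be an increase of 0.67 HDD/wk or 5 SDs/wk during the second 12 weeks dutasteride treatment". Neither section gives a standard deviation or a within-person correlation, and neither mentions regression to the mean.

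**The concern.** The reference window of the restricted-period comparison is the selection window. A patient counts as a responder when observed drinking in weeks 9-12 is at or below 40% of screening. Some patients pass that cut because those four weeks happened to be low for them. Weeks 21-24 are not selected in this way, so the group mean is expected to rise even if every patient's underlying level stays the same.

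If the non-inferiority test is run on this contrast, part or all of the margin is used up by selection before any real relapse occurs. The error runs against dutasteride. Aim 2A is meant to show clinical utility in a chronic relapsing disorder, and a lasting response could be reported as lost. The stated 80% power assumes an expected change of zero, which does not hold with this reference.

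**Working it through.** **Inputs from the protocol.** n = 40, power 80%, α = 0.05, limits of 5 SD/wk and 0.67 HDD/wk (2.C.9.b). Margin of 20% (2.C.9.a.2). Dutasteride response rate 49% (Table 1). Average screening intake about 48 SD/wk in the earlier trial in men (2.B.2).

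**1. The plan's own figure.** For a paired test with zero expected change, margin = (z for α + z for power) × SD of change / √n. No SD is given, so the formula can only be inverted:

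- One-sided 0.05: SD = 5 × 6.325 / (1.645 + 0.842) = 12.7 SD/wk. For HDD, 0.67 × 6.325 / 2.487 = 1.70 HDD/wk.
- One-sided 0.025: SD = 5 × 6.325 / (1.960 + 0.842) = 11.3 SD/wk. For HDD, 1.51 HDD/wk.

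Run forward, the standard error is 12.7 / 6.325 = 2.01, and power = Φ(5 / 2.01 − 1.645) = 80%.

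**2. What a non-zero expected change does.** With an expected rise δ, power = Φ((5 − δ) / 2.01 − 1.645):

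- δ = 1 gives 64%
- δ = 2 gives 44%
- δ = 3 gives 26%
- δ = 4 gives 13%
- δ = 5 gives 5%

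**3. How large the rise from selection is.** This needs assumptions, so it was simulated. Screening mean is 48 SD/wk. The ratio of a 4-week mean to screening is lognormal (log-SD 0.6-1.2), with a stable personal part and a transient part, and 49% meet the 60% cut. Weeks 21-24 keep the stable part and draw a fresh transient part, so the response is fully maintained. Each trial has 40 responders and a paired t bound (one-sided 0.025 for SD 11.3, otherwise 0.05). The comparator uses the same responders with a 4-week reference block that played no part in selection.

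| SD of change (SD/wk) | Apparent rise (SD/wk) | Pass, 5 SD/wk limit: weeks 9-12 / unselected reference | Pass, 20% margin: weeks 9-12 / unselected reference |
|---|---|---|---|
| 11.3-12.7 | 3.4-6.1 | 3-31% / 70-79% | 0.1-0.7% / 23-43% |
| 8 | 2.1-2.9 | 57-74% / 96% | 5-6% / 49-68% |
| 6 | 1.4-1.8 | 91-93% / over 99% | 17-23% / 64-84% |
| 4 | 0.7-0.9 | over 99% / 100% | 58-79% / 88-98% |

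The simulated rates differ somewhat from the formula in step 2 because responders' changes are skewed.

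**4. Separating selection from a small margin.** With no rise at all, a reference of 12 SD/wk and SD 12.7, the 20% margin is 2.4. Power is then Φ(2.4 / 2.01 − 1.645) = 33%. Part of the low pass rate under the 20% margin is therefore limited power at n = 40. The difference between the two figures in each cell is the part due to selection.

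**5. Whether the two margins agree.** 5 / 0.20 = 25 SD/wk and 0.67 / 0.20 = 3.35 HDD/wk. From a screening mean of 48, responders average at most 0.40 × 48 = 19.2 SD/wk in weeks 9-12, and 20% of that is at most 3.84. The two statements do not agree if weeks 9-12 are the reference.

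**6. The other reading of the reference.** If the reference is all 12 weeks of phase 1, and drinking is assumed higher in weeks 1-8, the simulated test passes in about 92-98% of runs near the implied SD. It is then lenient.

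**The case against.** The strongest objection is that the plan never ties the non-inferiority test to the restricted-period contrast. That contrast is introduced as an addition to the time series. The margin refers to phase 1 drinking without naming weeks, and step 5 shows that 5 SD/wk and 0.67 HDD/wk look more like whole-phase levels. This stands, and the conclusion must be conditional. It does not remove the problem. The weeks 9-12 contrast is expressly planned, the test sentence follows it closely, and the whole-phase reading brings a bias the other way.

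A second objection is that the result depends on an unstated SD. This also stands. A reader might infer that a maintained response would usually fail whatever the variability. The documents do not support that, because at a change SD of 6 the 5 SD/wk test passes in 91-93% of runs. The 11-13 is back-solved from a sentence that does not say it concerns 4-week means.

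Third, the bias cannot create a false claim of maintenance, and the plan has other evidence: end-of-phase proportions without heavy or hazardous drinking, and PEth change from baseline. These soften the consequence but do not correct the test.

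Fourth, the inputs are approximate. The 48 SD/wk comes from men only, whereas this trial expects 35% women with a lower entry threshold. The effect on HDD/wk was not quantified.

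**Conclusion.** The concern holds in a conditional form. The overlap between selection window and reference window is exact, nothing in the plan corrects for it, and the direction is toward concluding that the response was not maintained.

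If the non-inferiority test is run on this contrast at the SD implied by the Aim 2a figures, a fully maintained response would fail in most trials under either margin. At a change SD of about 8 the 5 SD/wk test loses roughly 20 to 40 percentage points. At about 6 or less it is little affected, while the 20% margin still loses much of its power to selection.

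These sizes rest on the assumed screening mean, the 49% response rate and the lognormal model. The existence and direction of the bias need only some transient variation within patients. It should be corrected before analysis.

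A reader might also infer that weeks 13-16 can simply replace weeks 9-12 as the main reference. They cannot. That would compare phase 2 with itself, and a relapse at week 13 would tend to be called maintained.

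**What to change.** 1. Do not base the maintenance conclusion on weeks 9-12 as the reference. Keep that contrast as descriptive, and say that selection on the same weeks inflates the rise.
2. Judge maintenance mainly on weeks 21-24 against screening: the mean reduction, and the proportion still reduced by at least 60%, each with a 95% CI. State that the proportion will fall below 100% through regression to the mean alone, and define beforehand what result will count as maintained.
3. Report weeks 21-24 against weeks 13-16 from the TLFB as supportive only, because it would hide a relapse right after week 12.
4. State which analysis, reference window, margin (20% or 5 SD/wk) and sidedness carry any formal non-inferiority test. State that the 80% power for Aim 2a assumes zero expected change and does not hold with a weeks 9-12 reference.

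The cost is a change of wording, a little more analysis and a less favourable power statement. TLFB data are already collected at screening and at every biweekly visit.

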At the end of phase 1 treatment week 12 (visit 8) and phase 2 treatment week 24 (visit 14), subjects will complete a series of questionnaires and be interviewed by research staff concerning their alcohol consumption and alcohol-related symptomatology. For subjects who withdraw early and do not wish to continue with study visits/procedures, end-of-treatment evaluations will be administered at the time of withdrawal. Such subjects will also be invited to participate in-person or by telephone to provide drinking data for the 12-, 24-week time points in order to include this data in intent to treat analysis of the treatment phase.

2.C.4.d. Visits 15 and 16 (3- and 6-month Post-treatment Assessment): To evaluate the durability of treatment effects, patients will be invited to return to the clinic for a post-treatment assessment 3 and 6 months after completion of treatment (if unable to come in person a telephone interview will be conducted). Subjects will be contacted 6-8 weeks after end of treatment and following the 3-month follow-up visit to remind them of their follow-up appointment dates, reinforce maintaining their written drinking diary and to remind female subjects of the importance of continued use of effective contraception for 6 months following treatment. At each follow-up visit, subjects will complete self-report questionnaires and will be interviewed by the research staff. Blood samples for measurement of serum PEth, and 3α -diolG will be obtained. Subjects will be paid \$50 for participating in each post treatment visit.

2.C.5. Medical Management: A study physician will meet with each subject at the beginning of treatment. The PI will consult at least weekly with study staff to monitor potential study-related side effects and will be available to personally evaluate subjects with severe or persistent adverse effects. At each treatment encounter, subjects will receive brief counseling as part of medical management, described below.

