For the phase 1 comparison of dutasteride and pbo over time, efficacy analyses will be performed using generalized linear mixed (GLMM) models implemented in SPSS. GLMM incorporates within subject correlation effects important in examination of repeated measures, can incorporate multiple covariates, interactions, random and fixed effects, nonnormal distributions, and is often recommended for designs such as proposed (Mallinckrodt C 2017). Medication group will be treated as a factor and treatment week as a continuous covariate. Sex, smoking status, treatment goal (stop vs. reduce drinking), and use of concurrent medication for co-morbid psychiatric conditions will also be examined as baseline between-subject covariates. Medication group, week, and the other covariates will be modeled as fixed effects, and the intercept will be modeled as random effects. For the outcome HDD/wk a binomial distribution with logit link will be used where the number of HDD during the week will be the numerator and number of observed days the denominator. For the outcome SD/wk a negative binomial distribution with log link will be used. An interaction term between medication group and the week term(s) will be used to evaluate whether the efficacy of dutasteride compared to pbo in reducing drinking varies over time. Interaction effects of sex and treatment condition will also be examined. Pretreatment drinking will be controlled using baseline TLFB drinking data as a covariate. The robustness of results will be evaluated by running the model under three different conditions: 1) modified intention to treat using all available outcome information from subjects with at least 1 post-randomization visit, 2) data from 12-week per protocol completers, and 3) multiple imputation using 10 imputed data sets with weekly drinking and baseline covariates thought predictive of the outcomes or missingness included in the imputation phase.

For aim 2, phase 2 outcomes, the within-subjects analysis will compare drinking during phase 1 against phase 2 for three groups: a) patients responsive to dutasteride in phase 1 and continuing on dutasteride for an additional 12-weeks in phase 2, to examine whether the response is maintained with continued treatment; b) phase 1 non-responders crossed over from pbo in phase 1 to dutasteride in phase 2 to provide a second contrast using an A-B design of the efficacy of dutasteride compared with pbo; and c) phase 1

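### The Aim 2A non-inferiority test has no analysis set and no rule for dutasteride responders who leave in phase 2 and are not reached for week-24 data, a gap that favours a finding of maintained response

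*Combined protocol and SAP*

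**What the plan says.** Section 2.C.9.a.2 (Efficacy, the paragraphs on aim 2) gives two analyses for dutasteride responders who continue on dutasteride. The first is an interrupted time series fitted as a mixed model. The second sets the end of one phase against the end of the other: "restricted period analysis focusing on the average of the last 4 weeks of phase 1 compared to average of the last 4 weeks", the latter taken from phase 2. The decision rule is non-inferiority: "For the first group, dutasteride responders, a non-inferiority test will be used where the non-inferior margin will be 20% above the drinking levels". The reference is each patient's phase 1 drinking.

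Section 2.C.9.b states the limit in absolute terms, for 40 responders at 80% power and α = 0.05: "the non-inferior margin limit would be an increase of 0.67 HDD/wk or 5 SDs/wk during the second 12 weeks dutasteride treatment". It makes no allowance for loss during phase 2.

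Missing data appear in two places. In the phase 1 paragraph of 2.C.9.a.2, "The robustness of results will be evaluated by running the model under three different conditions": modified intention to treat, 12-week completers, and multiple imputation. These are not repeated for aim 2, and no 24-week set is named. In section 2.C.4.c, on people who withdraw early: "Such subjects will also be invited to participate in-person or by telephone to provide drinking data for the 12-, 24-week time points". The stated purpose is to bring those data into the intent-to-treat analysis.

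**The concern.** Aim 2A is meant to show clinical utility in a disorder that the protocol describes as chronic and relapsing. Leaving treatment may be one way that relapse shows itself. In a superiority comparison, losing patients usually costs power. In a one-group test that drinking has risen by no more than a margin, losing those who relapsed moves the estimate toward the claim.

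A responder who leaves and is not reached has no weeks 21-24 average, so the restricted-period comparison drops that patient. The mixed model keeps the weeks before exit, but it fills in the rest on the assumption that, given those weeks, the patient would have continued like the patients who stayed. With no set and no rule written, the analysis could answer whether retained responders kept their response, while Aim 2A asks about responders.

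**Working it through.** **Inputs from the protocol.**
- Aim 2A: n = 40, 80% power, α = 0.05 with sidedness not stated, limit +5 standard drinks (SD)/week (2.C.9.b).
- Drinking level: a first-trial average of about 48 drinks/week (2.B.2). A 60% cut gives 0.40 × 48 = 19.2, so full return is +28.8 and half return is +14.4.
- Loss: no phase 2 rate is given. As proxies, phase 1 plans 190 randomized and 160 completing, 30/190 = 15.8% (2.C.2). The first trial had 107 completers, so 35/142 = 24.6% of those randomized were lost, or 28/135 = 20.7% of its modified intention-to-treat set (2.B.2).

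**The plan's own limit.** It cannot be reproduced, because no standard deviation of within-patient change is given. Solving backwards with margin = s(z₁₋α + z₀.₈₀)/√n: s = 5 × √40 / (1.645 + 0.842) = 12.7 at one-sided 0.05. The exact t version gives 12.5, which is used below. At one-sided 0.025 the exact value is 11.0.

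**True mean rise, stayers unchanged.** Rise = (leavers/40) × 28.8.
- 6 leavers: 4.32. Exactly 16% loss: 0.16 × 28.8 = 4.61.
- 7 leavers: 5.04. 8 leavers: 5.76.
- The 5 drinks/week limit is crossed at 5/28.8 = 17.4% loss. With half return it is crossed only at 5/14.4 = 34.7%.

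**Chance of claiming non-inferiority at weeks 21-24, 7 leavers with full return, one-sided 0.05.** With nobody retrieved, the test uses 33 stayers: standard error = 12.5/√33 = 2.18, 5/2.18 = 2.30, critical t = 1.69, so the chance is roughly Φ(0.60) = 0.73. Simulation gives:

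| Leavers retrieved (of 7) | Claim rate |
|---|---|
| 0 | about 73% |
| 1 | about 55% |
| 3 | about 24% |
| 7 | about 1% |

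At one-sided 0.025 the rates for 0, 3 and 7 retrieved are about 72%, 15% and 0.3%. For 8 leavers at one-sided 0.05 they are about 72% with none retrieved, 11% with four and under 1% with all.

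**The percentage margin.** Five drinks/week is 20% of 25, whereas 20% of 19.2 is 3.84. On that reading the margin is crossed at 3.84/28.8 = 13.3% loss. Six unretrieved leavers (true rise 4.32) still give a claim rate of about 54-55%: standard error = 12.5/√34 = 2.14, 3.84/2.14 = 1.79, critical t = 1.69, Φ(0.10) = 0.54.

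**Weeks before exit.** The planned mixed model was not run. A simple average of all observed phase 2 weeks serves as a rough stand-in, with 6 unretrieved leavers at +28.8 and a true weeks 21-24 rise of exactly 5 (stayers +0.8). The claim rate is about 72% if no relapse week is recorded before exit and 42% if two are. This average covers all of phase 2, so it is not a pure test at weeks 21-24.

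**The case against.** A reader might infer that relapsing leavers simply fall out of the test. The documents do not support that. Section 2.C.4.c plans retrieval of week-24 data and names its intent-to-treat use. Visits may be remote. The timeline follow-back at the 3- and 6-month follow-ups (2.C.6.b.4) covers each day since the last visit, so weeks 21-24 could be recovered there too. The mixed model, listed before the restricted comparison, also keeps relapse recorded before exit. Retrieving about half of the leavers removes most of the excess in the tables above.

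A reader might also infer that the plan's own attrition breaches its limit. Against 5 drinks/week it does not: about 16% loss with full return gives 4.3 to 4.6. With half return and 10 leavers the rise is 10/40 × 14.4 = 3.6, so a maintained claim there is correct against that limit. The loss proxies come from newly randomized patients, and the first-trial figure of 24.6% includes seven men who never returned after randomization. Responders who reached week 12 may leave less often. The 48 drinks/week comes from an all-male trial, whereas this one expects 35% women.

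All of this limits the size of the effect. It does not supply the rule. Retrieval is an invitation with no expected yield, neither Aim 2A analysis is said to use its results, and nothing covers those who decline.

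**Conclusion.** The gap stands: no Aim 2A analysis set is named, and nothing says how responders who leave and are not reached enter the test. Because this is a non-inferiority test, the available-data default favours the claim, so this is more than missing detail.

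The size is conditional. An error against the 5 drinks/week limit needs about 17% or more lost, near-full relapse among leavers, stayers unchanged and incomplete retrieval. Under those assumptions the false-claim rate runs from about 73% with no retrieval to about 24% with three of seven retrieved, and about 1% with all. Against 20% of 19.2 drinks/week, the planned phase 1 loss rate is already enough if leavers relapse fully. Phase 2 loss, relapse size and retrieval are all assumptions. It would go too far to say that the plan has no control of a false maintained finding: that depends on how many relapsed leavers stay unreached. The plan should be amended on this point before the Aim 2A analysis.

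**What to change.** In the aim 2 paragraphs of 2.C.9.a.2:

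1. Define the Aim 2A set as all phase 1 dutasteride responders who enter phase 2.
2. State that timeline follow-back data retrieved under 2.C.4.c enter both the time series and the last-4-weeks comparison.
3. Where weeks 21-24 are still missing, prespecify a conservative analysis: multiple imputation shifted toward the patient's own pre-treatment SD/week and heavy drinking days/week, with a tipping-point range up to full return.
4. Report the available-data result beside it. If non-inferiority does not hold across plausible shifts, limit the conclusion to responders who were retained or reached.

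Full return to baseline should not be the sole deciding analysis. With 6 unreached leavers all set to +28.8 and no true change in anyone, it would claim maintenance only about 4% of the time (s = 12.5, one-sided 0.05), against the planned 80% power.

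The cost is analysis-plan wording and one extra imputation analysis, with no new patients or visits. The downside is a possibly narrower conclusion on maintenance if many leavers cannot be reached.
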